# additional lab assessments for hepatic aminotransferases and haemoglobin will be performed at the patient’s general physician for safety reasons, reports will be faxed to the clinical site on a monthly basis

1.1 Trial objectives

Primary [Objectives/ Endpoints]

Determine whether mPAP of SSc patients with borderline-PAH (mPAP 21-24 mmHg, TPG \geq 11 mmHg) can be reduced by 3 mmHg (absolute change baseline vs. 6 months; equals 15%) by treatment with ambrisentan 10 mg/die (may be initiated with 5 mg/die and escalated to 10 mg/die) over 6 months (primary endpoint) compared to baseline and placebo.

Secondary Objectives

1. Determine whether exercise induced elevated mPAP-values ($>$ 30 mmHg without left heart or severe lung disease or systemic arterial hypertension) and further measures of exercise capacity, symptoms and quality of life can be reduced by ambrisentan 10 mg/die over 6 months
2. Analyze if the progression (adverse events, hospitalization, initiation of pulmonary hypertension treatment) of borderline-PAH to manifest PH can be avoided by ambrisentan-treatment (descriptive, observational)
3. Assessment of tolerability and safety

1.2 Trial design

This is a monocentric, randomized, controlled, double-blind study. Male or female SSc patients with borderline PAH will be randomized into two groups: Ambrisentan group and Placebo group. The primary endpoint will be the change of mean pulmonary arterial pressure between baseline and after 6 months compared to placebo.

2 Analysis of data quality

This analysis will be performed before unblinding the therapy arms.

1. For all variables at baseline, after 3-months and 6-months descriptive statistics mean standard deviation, median, IQR, min max, boxplot inspections of outliers for continuous variables and frequencies for categorical variables. Validation/correction will be performed by queries.

2. Calculation of differences for the parameters mPAP and all secondary endpoints. Descriptive statistics as in 1. for the differences to evaluate plausibility of the data.
3. Control of inclusion and exclusion criteria and withdrawal criteria, definition of patients to be excluded if applicable.
4. Control of laboratory values (and comparison to normal values)

3 Closure of the database and unblinding of treatment groups

1. After all data quality and plausibility checks have been performed and queries haven been answered
2. Database lock will be signed by data management, statisticians, principal investigator and trial coordinator
3. Data Transfer from open clinica to SPSS
4. Unique labeling of all major variables for the statistical Evaluation
5. Data dictionary
6. Merging of the data with the randomization list/group allocation

4 Analysis sets

4.1 Definitions

All patients randomized and treated will be valid for the intention-to-treat analysis population. A randomized patient is valid for the intention-to-treat, if at least one dose of study medication was administered. A patient is valid for per-protocol analysis, if the patient has an adequate hemodynamic measurement at baseline and after 12 weeks or if withdrawn due to lack of efficacy, who has an adequate hemodynamic assessment at any time post-baseline up to 12 weeks, and shows no major protocol deviation.

Major protocol deviations are:

1. Patients who do not meet the inclusion criteria
2. Administration of study medication not according to protocol (e.g. compliance less than 80% or greater 120%)

The above specifications of the analysis populations are in accordance with the recommendations given in the ICH-E9 Guideline “Note for guidance on statistical principles for clinical trials”.

The safety set comprises all patients who have been included in the study.

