## 1.1 Flow Chart/ Trial Schedule

	Randomized; double-blind controlled study including 38 patients with “borderline-PAH”				
Assessment	Screening “borderline-PAH” day -28/-1 Visit 1*	Baseline o day 1* Visit 2	After 3 months/ 90 days ± 2weeks Visit 3	After 6 months/ 180 days ± 2weeks Visit 4*	30±7 days Follow-up by phone
Written Informed Consent, obtained before any study procedure	X				
Check of eligibility criteria	X	X			
Demographics (height)	X				
Medical History	X				
Randomization		X			
Physical Examination	X	X	X	X	
SSc characteristics		X		X	
Modified Rodnan Skin Score and Symptoms of Scleroderma		X		X	
Vital Signs (blood pressure, heart rate, oxygen saturation, body weight)	X	X	X	X	
WHO functional class	X	X	X	X	
Electrocardiogram		X	X	X	
Pulmonary function tests: DLCo, DLCo/VA, FVC, FEV1, TLC, residual volume; blood gas analysis		X		X	
Local lab assessment #	X	X	X	X	
Pregnancy test (serum or urine)	X	X	X	X	
Echocardiography	X	X		X	
Right heart catheterization** (RHC), at rest, during exercise	X			X	
Quality of life Questionnaire SF-36		X		X	
6MWD, Borg Dyspnea Index		X	X	X	
Adverse events (AE)		X	X	X	X
Concomitant medication	X	X	X	X	
Concomitant disease	X	X	X	X	X
Study medication and Diary hand out or check		X	X	X	

o In borderline-PH-patients the screening assessment of PH screening (screening study, accepted by the Ethics committee University of Heidelberg) may be used as baseline examination for the randomized, double-blind part of the study when the screening assessment is not older than 28 days.

\* according to hospital practice possible in-hospital stay

\*\* Baseline-RHC may be up to 6 months old at inclusion, continuous ECG, CO and SvO2 recording during haemodynamic investigations

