6.3 Secondary variables

6.3.1 Efficacy

- (1) Analyze if in patients with SSc and borderline-PAP an improvement by treatment with ambrisentan 10 mg/die over 6 months is show in:
- (2) 6-Minute-walking test
- (3) Echocardiography: right atrial area (RA-area), right ventricular area (RV-area), Tei, Tricuspid Annular Plane Systolic Excursion (TAPSE), systolic pulmonary arterial pressure (sPAP), right ventricular pump function, left ventricular pump function,

- (4) Lung function tests: forced expiratory flow (FEV_1), total lung capacity (TLC), diffusion-limited carbon monoxide (DLCo), DLCo/alveolar volume (VA), forced vital capacity (FVC), forced expiratory volume in one second (FEV_1), residual volume
- (5) Borg Dyspnea Index
- (6) WHO-functional class
- (7) further invasively measured hemodynamic parameters evaluated by RHC: right atrial pressure, pulmonary vascular resistance, cardiac output (CO), cardiac index (CI), PAWP, venous oxygen saturation (SvO_2) at rest and during exercise
- (8) Raynaud-syndrome and skin involvement, assessed by the modified Rodnan-Skin score and Symptoms of Scleroderma (descriptive)
- (9) WHO functional class
- (10) Laboratory parameters (NT-proBNP)

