7.1 Missing values

Variables with more than 20% missing values will be excluded. For all others, a complete case data analysis for each variable will be performed. No imputation method will be applied.

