8.5 Efficacy Analysis primary parameter

The main parameter is the mPAP after 6 months compared to baseline. The differences will be compared between treatment and placebo group along with baseline mPAP as covariate using a covariance analysis, if the assumptions for a covariance analysis are fulfilled. Otherwise the individual differences of baseline mPAP and 6 months mPAP will be compared between therapy groups by robust comparisons of means as implemented in JMP14.

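### The per-protocol set in SAP 4.1 is tied to haemodynamics at 12 weeks, when no right heart catheterisation is scheduled and the endpoint is 6-month mPAP

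*SAP*

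**What the plan says.** SAP 4.1 gives two routes into the per-protocol set, both subject to there being no major protocol deviation. The main route applies "if the patient has an adequate hemodynamic measurement at baseline and after 12 weeks or if withdrawn due to lack of efficacy"; the clause on withdrawal opens the second route, for a patient "who has an adequate hemodynamic assessment at any time post-baseline up to 12 weeks". SAP 4.2 assigns the efficacy analyses to the intention-to-treat set and uses the per-protocol set for a sensitivity analysis of the primary endpoint. No other sensitivity analysis is named. The robust comparison of means in SAP 8.5 replaces the covariance analysis if its assumptions fail; it is not a second, parallel analysis.

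The endpoint is set at 6 months. SAP 1.2 states: "The primary endpoint will be the change of mean pulmonary arterial pressure between baseline and after 6 months compared to placebo". SAP 8.5 states: "The main parameter is the mPAP after 6 months compared to baseline". On missing data, SAP 7.1 excludes variables with more than 20% missing values and then says: "For all others, a complete case data analysis for each variable will be performed". It applies no imputation.

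In the protocol flow chart (section 1.1), the row "Right heart catheterization (RHC), at rest, during exercise" is marked at Visit 1 (screening) and Visit 4 (6 months) only.

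**The concern.** A per-protocol set should contain patients who followed the plan and have the measurement on which the endpoint rests. Here membership depends on a haemodynamic measurement at a time when the plan takes none, and the 6-month value that the analysis needs is not mentioned. If the rule is applied as it most naturally reads, the set is empty unless someone happens to have had an unscheduled catheterisation. The sensitivity analysis could then be run only by departing from the written definition. If that departure is decided after unblinding, membership of the set is no longer pre-specified.

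The withdrawal route has a separate defect. It admits patients on an early measurement, but neither SAP 7.1 nor SAP 8.5 has a use for that measurement.

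**Working it through.** **Inputs**
- Per-protocol time point: 12 weeks (SAP 4.1).
- Visit 3: 90 days ± 2 weeks. Visit 4: 180 days ± 2 weeks (protocol flow chart).
- RHC marked at Visits 1 and 4. Echocardiography marked at Visits 1, 2 and 4. Neither is marked at Visit 3 (protocol flow chart).
- Planned patients: 38 (protocol, Sample Size). This follows from the stated 15 per group and 20% drop-out: 15 / (1 − 0.20) = 18.75, rounded up to 19 per group, and 2 × 19 = 38. It serves here only as a denominator.

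**Step 1: what counts as haemodynamic.** SAP 6.3.1, item 7, speaks of "further invasively measured hemodynamic parameters evaluated by RHC". SAP 6.3.2 also places its haemodynamic measures during RHC, SAP 8.1 lists mPAP under haemodynamics, and SAP 8.6.1 lists haemodynamics and vital signs as separate items. The blood pressure and heart rate taken at Visit 3 therefore do not meet the rule.

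**Step 2: the calendar**
- 12 weeks: 12 × 7 = day 84.
- Visit 3: 90 ± 14 = days 76 to 104, which is 76/7 = 10.9 to 104/7 = 14.9 weeks. The window contains day 84. Scheduled RHCs: 0.
- Visit 4: 180 ± 14 = days 166 to 194, which is 166/7 = 23.7 to 194/7 = 27.7 weeks. This is the only scheduled post-baseline RHC.
- Distance from day 84 to Visit 4: 166 − 84 = 82 days at the earliest, 180 − 84 = 96 at the nominal day, 194 − 84 = 110 at the latest.

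**Step 3: what the 12-week phrase means.** Two readings are possible.
- *A fixed time point.* SAP 1.2 uses the same construction for the 6-month visit, and SAP section 2, item 1, uses it for the 3-month visit: "For all variables at baseline, after 3-months and 6-months". The second route in SAP 4.1 treats week 12 as the end of the assessment period. This is the natural reading. Scheduled RHCs that satisfy it: 0, so 0 of 38 patients qualify from scheduled measurements.
- *Any time later than week 12.* The Visit 4 RHC then qualifies. SAP 7.1 and 8.5 restrict the analysis to patients with a 6-month mPAP. Patients with an RHC later than week 12 who also have a 6-month mPAP are the patients with a 6-month RHC. That is the same sample as under a definition written for 6 months, so the change in the estimate is 0.

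**Step 4: the withdrawal route.** A patient admitted only through this route, with no 6-month mPAP, has no value for the SAP 8.5 analysis, and none is imputed. Observations added: 0 on either reading.

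**Step 5: the same period elsewhere.** Protocol exclusion criterion 5 refers to a study period of 12 weeks, while the Trial Design section and the flow chart give 6 months. The two statements conflict whatever is decided about SAP 4.1.

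**The case against.** The strongest reply is that nothing reported would change. The primary analysis uses the intention-to-treat set, SAP 8.5 fixes the analysed variable as 6-month mPAP, and SAP 7.1 makes the analysis complete-case. Taken literally, a measurement on days 166 to 194 does come after week 12, so the text can be followed. Nobody would carry out a rule that empties the set, and the blinded data review in SAP section 2, item 3, would bring the problem to light. On this view it is an editorial slip.

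Much of that stands. The zero count holds only on the fixed-time-point reading, and the workable reading gives the same estimate as corrected wording. But the workable reading goes against the SAP's own usage, and a definition that can be applied only by setting that usage aside has not properly been pre-specified. The blinded review is an opportunity to correct the text; it does not itself correct it.

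A second reply is that the withdrawal route was a deliberate way of keeping patients who leave for lack of efficacy, and that it should be extended to 6 months, not removed. The sponsor may prefer that. It would then have to say how the early value enters the analysis, because under SAP 7.1 it does not enter at all. As the plan stands, removing the route loses no data.

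Third, SAP section 2 refers to withdrawal criteria that the protocol text available for this review does not include, so an RHC at early termination cannot be ruled out. The zero count therefore describes the flow chart. Such an RHC would bear on withdrawn patients; it would not supply a 12-week measurement for those who complete the trial.

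**Conclusion.** The concern holds. The time point in SAP 4.1 matches neither the RHC schedule nor the endpoint. On the natural reading, 0 of 38 planned patients qualify from scheduled measurements. On the looser reading the per-protocol estimate is unchanged. On both, the withdrawal route contributes no observations from patients without a 6-month mPAP.

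The effect is confined to the per-protocol sensitivity analysis. The intention-to-treat primary analysis and the sample size are not touched. The text should be corrected, but the error does not threaten the trial's main result.

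The conclusion assumes that the flow chart is the complete RHC schedule and that haemodynamic means measured by RHC, as the SAP uses the word. How many of the 38 patients would enter a corrected set depends on actual drop-out and deviations and is not predicted here.

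**What to change.** Before unblinding, replace the 12-week text in SAP 4.1 with: *an adequate resting RHC at baseline and at the 6-month visit, and no major protocol deviation*. Specifying rest follows the protocol, whose 21–24 mmHg range in the Indication section is at rest and which makes exercise mPAP a secondary objective. Remove the 12-week withdrawal route, or state that those patients are only listed. At the blinded review in SAP section 2, the sponsor should settle and record whether an RHC outside the Visit 4 window, or a breach of an exclusion criterion, removes a patient from the set. If unblinding has already taken place, report the definition actually used as a departure from SAP 4.1.

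Separately, reconcile the study period in protocol exclusion criterion 5 with the 6-month period in the Trial Design section.

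The cost is one sentence in the SAP and one wording reconciliation in the protocol, with no added visits, procedures or patients. Patients who withdraw without a 6-month RHC will not be represented in the per-protocol analysis. That is already so under SAP 7.1, and it should be stated when the analysis is reported.

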4.2 Application

Efficacy analyses will be performed for the intention-to-treat analysis set. A sensitivity analysis for the primary endpoint will be performed with the per-protocol set.

Safety analyses will be performed with the safety set.

5 Trial centres

Zentrum für pulmonale Hypertonie, Thoraxklinik am Universitätsklinikum Heidelberg

6 Analysis variables

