### **Sample Size**

In this randomized, controlled, double-blind study patients with borderline PAH will be randomized into two groups: one group receiving ambrisentan and one Placebo. The main comparison will be the difference in treatment effect between ambrisentan arm and placebo. The primary endpoint will be the change of mean pulmonary arterial pressure between baseline and after 6 months compared to placebo.

Based on previous data and the inclusion criteria we expect a baseline mPAP of 20 mmHg, a mean reduction of 3 mmHg (equals 15%) with standard deviation of the difference of 2.5 mmHg. To reject the null hypothesis with 90 percent probability if the means of the mPAP differ by at least 3 mmHg (17 vs. 20 mmHg, 15%) a sample of 15 patients in each group is required, according to the two-tailed Student's t-test, with a type I error of 0.05 (two-sided) and equal standard deviations of 2.5 mmHg in both patient groups.

EudraCT: 2014-001882-28	3.1 Version 29.04.2016 final	EDITA
-------------------------	------------------------------	--------------

Due to the fact that the borderline-PAP-group is defined by an mPAP of 21-24 mmHg the sample will have a small standard-deviation. The effect of lowering the mPAP in SSc-APAH-patients by 15% has been reached in several studies as in Klinger et al. (2011). In order to cover a possible 20% drop-out rate, we will include 19 patients in each group = 38 patients in total.

The sample size was calculated by means of a two-sided two-sample t-test. Primary efficacy analysis will be performed by an analysis of covariance (ANCOVA) model including baseline scores as covariate, thereby yielding a power advantage over the standard t-test used for sample size calculation. The calculated sample size will thus provide 90% power or more.

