8.6.1 Efficacy

Secondary efficacy analysis comprises hemodynamics, vital signs, electrocardiogram, echocardiography, systemic sclerosis characteristics, laboratory parameters, pulmonary function, 6-minute walking distance, quality of life scales. For continuous variables the therapy groups will be compared with the same methods as for the primary parameter.

WHO functional class is supposed to either remain the same, improve by one or two categories, or deteriorate by one category in most cases. A change score (baseline minus end of study) will be calculated, which could go from -3 (class 4 at baseline and class 1 at end of study) to +1 (class 3 at baseline and class 4 at end of study). This will be analyzed using the Wilcoxon test.

For categorical variables Mc Nemar Tests will be applied.

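### The mPAP analysis labelled intention-to-treat is a complete-case analysis, and the one planned sensitivity analysis does not test the assumption about missing month-6 values

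*SAP*

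**What the plan says.** **Endpoint and analysis.** SAP 1.2: "The primary endpoint will be the change of mean pulmonary arterial pressure between baseline and after 6 months compared to placebo". SAP 8.5 compares the baseline to 6-month differences by ANCOVA with baseline mPAP as covariate.

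**Analysis set.** SAP 4.1: "All patients randomized and treated will be valid for the intention-to-treat analysis population". SAP 4.2 applies that set to efficacy and adds: "A sensitivity analysis for the primary endpoint will be performed with the per-protocol set". Per-protocol patients need adequate haemodynamics at baseline and after 12 weeks and no major deviation (entry criteria not met, or compliance outside 80-120%). A patient withdrawn for lack of efficacy can qualify with any adequate haemodynamic assessment up to 12 weeks.

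**Missing values.** SAP 7.1 drops variables with more than 20% missing. All others are analysed on complete cases, variable by variable, and imputation is ruled out.

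**Expected loss.** Protocol, Sample Size: "In order to cover a possible 20% drop-out rate, we will include 19 patients in each group".

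**Schedule.** Protocol 1.1 marks RHC at screening and month 6 only. Some secondary measures are also taken at month 3, for example "6MWD, Borg Dyspnea Index X X X" (baseline, month 3, month 6). For secondary efficacy, SAP 8.6.1 says: "For continuous variables the therapy groups will be compared with the same methods as for the primary parameter".

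**The concern.** A treated patient without a month-6 RHC belongs to the intention-to-treat set by definition but has no change score, so that patient leaves the primary ANCOVA. The estimate is then a completer estimate. It is valid for all treated patients only if those without a month-6 value would have resembled the completers of their own arm with the same baseline mPAP.

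Reasons for withdrawal, such as lack of efficacy or adverse events, can differ between an active and a placebo arm, so that assumption needs testing. The per-protocol analysis does not test it, because it selects patients on compliance and eligibility and fills in no missing value. If the two analyses agree, a reader may take this as robustness to withdrawal that neither has examined.

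**Working it through.** **1. The plan's own figures.** Inputs from Protocol, Sample Size: "if the means of the mPAP differ by at least 3 mmHg (17 vs. 20 mmHg, 15%) a sample of 15 patients in each group", "with a type I error of 0.05 (two-sided) and equal standard deviations of 2.5 mmHg in both patient groups", power 90%.
- Normal approximation: n = 2 × (1.960 + 1.282)² × 2.5² / 3² = 14.6, so 15 per group. This reproduces the stated figure. By exact noncentral t, 15 per group gives 88.7% power.
- Drop-out: 15 / 0.8 = 18.75, so 19 per group and 38 in total. The plan thus allows for about 4 of 19 per arm without the endpoint.

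**2. Completer analysis as planned** (15 per arm, two-sample t without the covariate)
- SE = 2.5 × √(2/15) = 0.913; critical t (28 df) = 2.048.
- Difference 3.0: t = 3.29, 95% CI 1.13 to 4.87. Difference 2.0: t = 2.19, significant.

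**3. All 19 per arm.** Assumptions not in the documents: 4 missing per arm, and missing placebo patients resemble placebo completers. Let D be the completer difference and x the mean benefit of the missing ambrisentan patients over placebo.
- Estimate = (15D + 4x)/19. With D = 3 and x = 0 this is 45/19 = 2.37. With 3 missing per arm it is 3 × 16/19 = 2.53.

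**4. Multiple imputation from the placebo arm** (Rubin's rules, no baseline covariate). In closed form, treating SD 2.5 as known:
- Ambrisentan variance = 6.25 + [15 × 4/(19 × 18)] × (D − x)².
- Within-imputation variance W = (ambrisentan variance + 6.25)/19.
- Between-imputation variance B = (4/19)² × 2 × 6.25/4 = 0.139. Both arms are imputed from the same placebo mean, so its error cancels.

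| D | x | Estimate | W | SE = √(W + B) | t |
|---|---|---|---|---|---|
| 3.0 | 0 | 2.37 | 0.741 | 0.938 | 2.52 |
| 3.0 | −1.4 | 2.07 | 0.837 | 0.988 | 2.10 |
| 2.0 | 0 | 1.58 | 0.695 | 0.913 | 1.73 |

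A simulated imputation that also draws the SD gives t = 2.46, 2.05 and 1.68 for these rows, against a critical value of about 2.05. Significance at D = 3 is therefore lost near x = −1.4. At D = 2 it is already lost at x = 0.

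**5. Dependence on method.** Holding the SE at the completers' 0.913, solve 3 − (4/19)δ = 2.048 × 0.913 = 1.870. This gives δ = 5.37 mmHg below ambrisentan completers, or 5.37 − 3 = 2.37 mmHg worse than placebo. Filling in one constant value tips at about 2.6. Both understate the uncertainty compared with step 4.

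**6. An extreme case.** Simulated with no true effect: the ambrisentan patients with the largest mPAP rises are the missing ones, and placebo loses equal numbers at random. Rejection is about 10% with 2 missing per arm and about 20% with 4, against a nominal 5%. This is a deliberately severe selection rule, not a forecast.

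**7. Month-3 measures (6MWD).** Assumptions: SD 80 m, true effect 30 m, correlation 0.7-0.9, and 60% drop-out after a month-3 fall of more than 40 m. In simulation, complete-case ANCOVA gives 27.9-28.4 m and a model using month 3 gives 29.9-30.1 m. With 17 per arm, SE = 80 × √(1 − r²) × √(2/17), which is 19.6 m at r = 0.7 and 12.0 m at r = 0.9. The gain of about 2 m is small against that.

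**The case against.** This is a 38-patient, single-centre proof-of-concept trial, and a completer analysis of an invasive endpoint is a common choice. The documents give no withdrawal rates by arm or reason, so neither the direction nor the size of any bias is known. That stands, and it is why the figures above are illustrations. It does not remove the gap, because the plan itself expects the loss.

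Four stronger readings are tempting, and the documents do not support them:
- **Every patient who stops treatment leaves the analysis.** A missing month-6 RHC removes a patient; stopping drug does not. The supplied text does not say whether patients who stop are still catheterised at month 6.
- **The per-protocol set is always a smaller subset of the completers.** The 12-week clause in SAP 4.1 could admit a patient withdrawn for lack of efficacy. No RHC is scheduled then, so only an unscheduled one would trigger it, and its value would not be a 6-month value.
- **Month-3 data are never used, or could rescue the primary analysis.** They enter the data-quality review (SAP 2), the summaries at each visit (SAP 8.2) and vital signs by visit (SAP 8.6.2). No month-3 mPAP is scheduled, so they cannot replace a missing primary value.
- **The effect is overstated by a known amount.** The fall from 3.0 to 2.37 requires every missing ambrisentan patient to sit at the placebo mean.

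**Conclusion.** The concern holds for the primary endpoint. The analysis named intention-to-treat is a complete-case analysis, and nothing in the SAP varies the assumption about missing month-6 mPAP. Under the stated assumptions (15 completers and 4 missing per arm, SD 2.5, no baseline covariate), a 3.0 mmHg completer result survives placebo-like drop-outs (t about 2.5). It fails when they are about 1.4 mmHg worse than placebo. A 2.0 mmHg result fails already at the placebo mean (t about 1.7). Fewer missing values would weaken these effects.

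This is separate from the 20% exclusion rule in SAP 7.1; removing that rule would leave the gap open. The two do meet in one place: 8 of 38 missing is 21.1%, so the planned loss, read literally, would exclude mPAP itself. The illustration presumes that mPAP is still analysed.

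The month-3 point is minor. For 6MWD, Borg and vital signs, month-3 values are described but do not enter the specified efficacy comparison, and the expected gain from using them is small. Overall this is a worthwhile, cheap improvement; it does not show that the primary analysis is wrong.

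**What to change.** 1. Keep the primary ANCOVA, and state in SAP 4.2 and 7.1 that it uses patients with a month-6 RHC.
2. Add one sensitivity analysis on all randomised and treated patients. Multiply impute missing 6-month mPAP from the placebo arm given baseline mPAP, analyse with the same ANCOVA, and combine by Rubin's rules. Then shift the imputed ambrisentan values in prespecified steps until significance is lost, and report that shift. Amend the no-imputation sentence in SAP 7.1 to allow this.
3. Reconcile the 12-week haemodynamic criterion in SAP 4.1 with the 6-month endpoint and the RHC schedule. State how month-6 values obtained after stopping study drug are handled, if there are any.
4. Optional: for continuous outcomes measured at baseline, 3 and 6 months, use a repeated-measures model with the 6-month contrast as the result.

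Cost: SAP wording and some programming, with no new data or visits. The downside is a little more analysis work and a sensitivity estimate that may be less favourable than the completer estimate.
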